### 5.2. Adverse Events

The verbatim terms used in the CRFs by the investigator to identify adverse events (AEs) will be coded using the current Medical Dictionary for Regulatory Activities (MedDRA) maintained by the sponsor.

Therapeutic reach is the number of days after the last dose intake that a subject is still considered to be potentially affected by study drug. For JNJ-42165279, therapeutic reach is defined as 4 days. AEs during the double-blind treatment period will be summarized using the therapeutic reach. Therapeutic reach will only be applied to the end of double-blind treatment period or to subjects who discontinue during the double-blind treatment period.

A treatment-emergent AE (TEAE) is an event that is new in onset or increased in severity following treatment initiation. Any event with a start date and time after the first dose intake will be considered treatment-emergent. An event that starts prior to and ends after the initiation of study medication will be considered treatment-emergent only if the severity increases after the start of medication. An event that starts in the withdrawal or follow up period but within the therapeutic reach of 4 days of the double-blind treatment period will be considered treatment-emergent during the double-blind treatment period. Adverse events with onset date during the withdrawal/follow-up period outside the therapeutic reach of 4 days will be summarized separately.

- The number (%) of subjects with TEAEs will be summarized by system organ class and preferred term for each treatment group and study period. A summary will be created for the most common TEAEs ( $\geq 5\%$  incidence in either treatment group). Both of these summaries will also be provided for the enriched Safety analysis set.
- In addition, TEAEs will be summarized by severity and relationship to study drug for each treatment group and study period by system organ class and preferred term. For the summaries of AEs by severity/relationship to study drug, the observation with the most severe occurrence/closest relationship to study drug will be chosen if there is more than one incident of an adverse event reported during the treatment phase by the subject.
- The following TEAEs are considered to be of special interest in this study: severe headache, change in mental states, change in sensory function, change in motor function or coordination. The number (%) of subjects with TEAEs of special interest will be summarized by system organ class and preferred term for each treatment group and study period. Listings will be created with the results of neurological examinations following the incidence of these AEs.
- Data listings will be generated for all AEs, deaths, serious adverse events (SAEs), severe AEs and discontinuations due to AEs and AEs of special interest. These listings will not be limited to TEAEs but will also include any adverse events with onset before the start of study treatment or after the end of study treatment. If there is no data to present then the listing should be created and should state "No data to present".

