3. STUDY DESIGN AND RATIONALE

3.1. Overview of Study Design^a

This is a multi-center, double-blind, placebo-controlled, randomized, parallel-group study in subjects with MDD with anxious distress who have had inadequate response to SSRI/SNRI treatment. Subjects with MDD with anxious distress who have had treatment initiated with an SSRI/SNRI allowed by the protocol will be screened at the investigation site. Site assessments will be reviewed and verified by an independent central rater. The review by a central rater will include the clinical history of MDD, SSRI/SNRI treatment of adequate dose and duration for the current episode of depression, and current symptom severity on the HDRS₁₇. Assessments by qualified site personnel including the MINI, ATRQ, and HDRS₁₇ will be recorded for review and validation of the suitability of the subject for enrollment into the study by an independent central rater contracted by the sponsor. Subjects who meet the inclusion and exclusion criteria and are enrolled will be maintained on the SSRI/SNRI treatment throughout the study to determine whether adjunctive treatment with JNJ-42165279 can reduce symptoms of MDD with anxious distress. For each subject, the study will consist of three phases: a screening phase of up to 4 weeks, double-blind treatment phase lasting up to 11 weeks, and a 3-week post-treatment (follow up) phase. The double-blind treatment phase of the trial will consist of 3 periods. The first period is a placebo lead-in of double-blind duration, after which subjects will enter the treatment period when they will be randomly assigned to JNJ-42165279 or continuation on placebo for 6 weeks. Subjects who successfully complete the treatment period prior to the end of Week 11, will be treated with placebo for the remaining time of the double-blind phase of the study, which will vary depending on the duration of the placebo lead-in for the specific subject. The total study duration for each subject will be approximately 18 weeks. The end of study is defined as the date of the last visit of the last subject undergoing the trial. Investigators and subjects will

[figure not shown]
^a This section has been amended per Amendments INT-1 and 2.

remain blinded to the exact duration of the subject lead-in and withdrawal period during the entire study duration.

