11.3. Safety Analysis^a

All subjects receiving at least one dose of study drug will be included in the safety analysis. All safety analyses will be performed based on the safety analysis set, which will include all randomized subjects who receive at least 1 dose of study drug.

Adverse Events

The verbatim terms used in the CRF by investigators to identify adverse events will be coded using the Medical Dictionary for Regulatory Activities (MedDRA). All reported adverse events with onset during the double-blind treatment phase (i.e., treatment-emergent adverse events, and adverse events that have worsened since baseline) will be included in the analysis. For each adverse event, the percentage of subjects who experience at least one occurrence of the given event will be summarized by treatment group. Summaries will be provided for all subjects receiving at least one dose of study drug in this study, and will include adverse events from this study.

Summaries, listings, datasets, or subject narratives may be provided, as appropriate, for those subjects who die, who withdraw due to an adverse event, or who experience a severe or a serious adverse event.

Clinical Laboratory Tests

Laboratory data will be summarized by type of laboratory test. Descriptive statistics will be calculated for each laboratory analyte at baseline and at each scheduled time point, and for changes from baseline.

The number and percentage of subjects experiencing a laboratory result below or above normal reference ranges will be provided for each laboratory analyte by treatment group. Summaries will be provided for all subjects receiving at least one dose of study drug in this study.

A listing of subjects with any laboratory result outside the reference ranges will be provided.

12-Lead ECG

Heart rate and ECG intervals (RR, PR, QRS and QT) as well as corrected QT intervals according to Bazett's formula (QTcB) and Fridericia's formula (QTcF) from the 12-lead ECG will be summarized at baseline and at each scheduled time point and for changes from baseline using descriptive statistics.

The number and percentage of subjects with at least one occurrence of a treatment-emergent potentially clinically important QTc measurement (QTc value >450, >480, or >500 msec) or with a change from baseline in QTc >30 msec will be summarized by treatment group.

^a This section has been amended per Amendment INT-2.

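### Does the unexplained 4-day therapeutic reach in SAP 5.2 make the adverse-event comparison unsound?

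*SAP*

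**What the plan says.** SAP 5.2 defines therapeutic reach as the number of days after the last dose "that a subject is still considered to be potentially affected by study drug". It then fixes the value: "For JNJ-42165279, therapeutic reach is defined as 4 days". The reach applies only at the end of the double-blind treatment period or to subjects who stop during that period. An event that starts in withdrawal or follow-up but within the reach is assigned to the double-blind period. Events starting then but "outside the therapeutic reach of 4 days will be summarized separately".

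The main table of treatment-emergent events "will be summarized by system organ class and preferred term for each treatment group and study period". Events of special interest get the same layout: "The number (%) of subjects with TEAEs of special interest will be summarized", again by treatment group and period. All adverse events are listed, including those starting after study treatment ends.

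Protocol 11.3 is less detailed. It brings into the analysis "All reported adverse events with onset during the double-blind treatment phase" and says that "the percentage of subjects who experience at least one occurrence of the given event will be summarized by treatment group". On the word phase, Protocol 3.1 states: "The double-blind treatment phase of the trial will consist of 3 periods". These are the lead-in, the treatment period and the withdrawal period. The introduction to Protocol 11 leaves specifics to the SAP.

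**The concern.** Two things look wrong.

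- **The value.** Four days is 96 hours, and Protocol 1.1 has a measurement at 96 hours after the last dose. Mean white-cell FAAH activity was still well below predose, and mean plasma fatty acid amides were 1.3 to 3.1 times predose. A definition that turns on being potentially affected is a low bar, and these data seem to clear it. The SAP cites no basis for stopping at 4 days, and the protocol does not use the term.
- **The tables.** Protocol 11.3, read with Protocol 3.1, seems to promise a by-arm percentage over the whole phase, withdrawal included. SAP 5.2 splits the phase by period. A subject with the same event in both periods appears in both tables, so the tables cannot be added to give the number of subjects affected from first double-blind dose to end of withdrawal.

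Safety and tolerability belong to the primary objective, and the study resumed after a class-wide clinical hold (SAP 1.4). If a delayed drug effect were placed outside the double-blind table, the main safety comparison could understate it.

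**Working it through.** **The 4-day value.** Neither document gives a derivation, so it cannot be reproduced. It can be compared with the protocol's own Phase 1 data.

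*Enzyme.* Residual inhibition = 100% − activity as a percentage of predose (Protocol 1.1, study 42165279EDI1002):

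- 100 − 58.2 = 41.8%
- 100 − 28.3 = 71.7%

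These are preliminary group means over 25 to 100 mg from cohorts of six active subjects, with no separate 25 mg value. Protocol 3.2 ties near-maximal effect to more than 90% inhibition, so every group mean at 96 hours is below that level. No threshold for adverse events is given.

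*Plasma drug.* Protocol 1.1 gives a Day 6 to Day 1 AUC ratio of 1.44 at 100 mg once daily. Assuming simple one-compartment accumulation, R = 1 / (1 − f), where f is the fraction remaining after 24 h:

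- f = 1 − 1/1.44 = 0.306
- effective half-life = 24 × ln 2 / (−ln 0.306) ≈ 14 h
- 96 / 14 ≈ 6.8 half-lives, leaving 2^(−6.8) ≈ 0.9% of drug

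On this assumption, 4 days is a plausible clearance-based reach. The Phase 1 half-lives themselves are redacted.

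*What an enzyme-based reach would imply.* Assume one-exponential recovery from a nadir n to the 96-hour activity a, starting L days after the last dose: k = ln[(1 − n)/(1 − a)] / (4 − L), and the time to activity x is L + ln[(1 − n)/(1 − x)] / k. With a = 0.283 or 0.582, L = 0 or 1, and n from 0 to 0.105:

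| Target activity | Earliest | Latest |
|---|---|---|
| 80% of predose | 6.5 days | 27.0 days |
| 90% of predose | 8.9 days | 39.5 days |

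The answer depends almost entirely on the threshold and the scenario. The longer values would absorb the whole 14-day withdrawal period.

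**What moves between tables, for completers.** The double-blind period is 6 weeks (42 days) and withdrawal is 2 weeks (14 days; SAP 1.2), so the window is 42 + 14 = 56 days.

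- Inside the double-blind table: 42 + 4 = 46 days; 46/56 = 82%
- Outside it: 14 − 4 = 10 days; 10/56 = 18% of the window and 10/14 = 71% of withdrawal

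**Early discontinuers.** Subtracting 4 from the 7-to-21-day follow-up window (Time and Events Schedule, footnote b) suggests 3 to 17 days outside. SAP 2.4 does not work that way. If a subject never enters withdrawal, the double-blind period runs until follow-up starts, which is the day after the early-withdrawal visit. If no follow-up visit takes place, there is no follow-up phase and the last phase runs to last contact. The 3-to-17-day figure therefore cannot be used.

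**The combined count.** If a subjects have an event in one period and b in the other, the number with it in either lies between max(a, b) and a + b. This bound holds for any two-period tabulation and says nothing specific about this trial.

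**Protocol 11.3 against SAP 5.2.** Protocol 11.3 asks that events in the phase be included and summarized by treatment group. It does not say that periods must be pooled. SAP 5.2 includes the same events, by treatment group and period. A literal whole-phase table would mix pre-randomization placebo lead-in events into the arm comparison. A table starting at the first double-blind dose would be more useful, but it is not what Protocol 11.3 describes either. SAP 5.2 is also not wholly period-bound: its summary of events with at least 5% incidence names no period, and its severity and relationship rule takes the worst occurrence in the treatment phase, which SAP 1.2 defines as all three periods.

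**The case for a change.** The best case for a change is that a table not depending on the cut costs little and removes an arbitrary choice. No visit is scheduled between Day 63 and Day 77, so many onset dates near the cut will rest on recall. SAP 5.1 sets a missing onset day to the first of the month when double-blind drug began in an earlier month, which can carry an event across the cut. The Day 77 neurological examination comes about two weeks after the last active dose, and the events of special interest are largely neurological.

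Parts of this stand. No basis for 4 days is stated, the 96-hour data sit awkwardly with the SAP's own definition, and no table is clearly specified that counts each subject once over the two periods. But an event shifted across the cut moves from one planned summary to another and stays in the listings. Dates are recorded blind to arm, so there is no evident reason for the error to favor either arm. A combined table would also mix residual-drug events with withdrawal events, and the placebo arm does not separate those for a subject coming off active drug. Protocol 3.2 wants withdrawal symptoms explored, and the period split serves that aim. An analyst who wants the de-duplicated count can derive it from data already collected.

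**Conclusion.** No change to the plan is needed. The 4-day cut is a convention whose reason was not written down, and the available data do not show it to be wrong. Its effect is on where events appear: for completers, events starting in 10 of the 56 days (18%) move from the double-blind table to a separate summary. The safety comparison remains interpretable because those events are still summarized and listed. Splitting by period trades a single de-duplicated count for a cleaner view of withdrawal, which is reasonable in this design. A sentence giving the basis for 4 days would help the reader, and a supplementary combined table would do no harm, but neither corrects a faulty result or restores a dropped protocol commitment.

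This rests on the withdrawal summary being produced by treatment group, as the by-period rule in SAP 5.2 implies. It also rests on the Phase 1 enzyme data being no more than what the protocol shows: preliminary means without a 25 mg figure and without a stated link to adverse events. The plasma half-life of about 14 hours is illustrative and comes from 100 mg data. How many events would change tables cannot be worked out from the documents.

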### 5.3. Clinical Laboratory Tests

For each study period, descriptive statistics on actual values and changes from respective period baseline at each scheduled time point for hematology, chemistry, urinalysis and coagulation will be provided for the Safety analysis set. Laboratory summaries will be provided in Standard International (SI) units. All laboratory data will be listed for the All Subjects set.

Cross-tabulations (with classes for below, within, and above the central laboratory range) showing the shift of laboratory values from baseline to each scheduled time point and endpoint will be presented by treatment group and study period.

Clinical laboratory test values will be considered “treatment emergent markedly abnormal” (TEMA) using the criteria defined by the Sponsor (Johnson & Johnson Research & Development, LLC) listed in Table 3. The identification of TEMA laboratory values is based on baseline value (in any period) being missing or within the normal range and the corresponding post baseline value being markedly high/low as per the values in Table 3. If post baseline laboratory results are above the upper limit and the baseline value is below the lower limit, then the post baseline abnormality will also be considered TEMA. The same applies to the post baseline value being below the lower limit with the baseline value being above the upper limit.

The incidence of TEMA will be presented by treatment group and study period at each scheduled time point and endpoint.

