## 1.2. Trial Design

This is a multi-center, double-blind, placebo-controlled, randomized, parallel-group study in subjects with MDD with anxious distress who have had inadequate response to SSRI/SNRI treatment.

Subjects who meet the inclusion and exclusion criteria and are enrolled will be maintained on the SSRI/SNRI treatment throughout the study to determine whether adjunctive treatment with JNJ-42165279 can reduce symptoms of MDD with anxious distress.

[figure not shown]
For each subject, the study will consist of three phases: a screening phase of up to 4 weeks, a treatment phase lasting up to 11 weeks, and a 3-week post-treatment (follow up) phase. The treatment phase of the trial will consist of 3 periods. The first period is a placebo lead-in of 3 weeks for all subjects, after which subjects will enter the double-blind treatment period when they will be randomly assigned to JNJ-42165279 or continuation on placebo for 6 weeks. Subjects who successfully complete the double-blind treatment period will be treated with placebo during a 2-week withdrawal period. The total study duration for each subject will be approximately 18 weeks.

The end of study is defined as the date of the last visit of the last subject undergoing the trial. Investigators and subjects will remain blinded to the exact duration of the subject lead-in and withdrawal period during the entire study duration.

Approximately 143 subjects will enter the double-blind placebo lead-in period. At the end of the lead-in period, response status of the subjects will be assessed according to the double-blind response criteria based on reduction in HDRS17 relative to lead-in baseline. Both lead-in placebo responders and lead-in placebo non-responders will be randomly assigned in a 1:1 ratio to either 25 mg of JNJ-42165279 or placebo in the treatment period. The primary efficacy analyses will be based on the treatment period data from the lead-in non-responders (94 subjects).

An overall flow diagram of the study is shown in the figure below.

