## **2. GENERAL ANALYSIS DEFINITIONS**

The statistical analysis will be performed using SAS® version 9.3 or higher.

The analysis will include descriptive statistics, frequency tabulations, statistical analyses, graphical presentations and data listings.

Unless otherwise specified, descriptive statistics of continuous parameters will be summarized using the following statistics: number of observations, mean, standard deviation (SD), standard error (SE), minimum, median and maximum. Frequency tabulations will display the number of subjects and corresponding percentage, where the incidence is based on the number of subjects in each treatment group.

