### 2.4. Analysis Timepoints and Phases

Please refer to the time and events schedule in the latest version of the protocol for analysis timepoints per assessment.

**Baseline (reference time point):** for each of the Lead-in, DB Treatment and Withdrawal Period, the reference assessment, i.e. baseline, is the measurement the closest, and prior to the first study medication administration of that period. The baseline measurement may be taken from a scheduled or unscheduled visit.

**End Point for double-blind treatment period:** end point is defined as the last non-missing post-baseline observation during the double-blind treatment period. End point will be defined only for the double-blind treatment period.

Analysis phases will be constructed as follows:

Analysis Phase	Start Date/time	End Date/time
Screening	00:00 of the date of signing the informed consent	1 minute before the first study medication administration in the Lead-in Period
Lead-in Treatment Period	Date/time of the first study medication administration in the Lead-in Treatment Period	1 minute before the first study medication administration in the Double-Blind Treatment Period

		If the subject does not enter the Double-blind Treatment Period then use 23:59 of the day before the date of the first Follow-Up visit
Double-Blind Treatment Period	Date/time of the first study medication administration in the Double-Blind Treatment Period  If the subject takes the morning dose on the day of randomization prior to the randomization (i.e. a dose of the lead-in medication), the time of morning intake of the next day is not known. The start date of the double-blind treatment period will be the day after the day of randomization, and the time of intake will be imputed as 0:00.	1 minute before the first study medication administration in the Withdrawal Treatment Period.  If the subject does not enter the Withdrawal Treatment Period then use 23:59 of the day before the start of the Follow-Up period.
Withdrawal Treatment Period	Date/time of the first study medication administration in the Withdrawal Period	Day 77 visit or early withdrawal visit for subjects who dropout early.
Follow-up	00:00 of the date after the Day 77 visit or early withdrawal visit for subjects who dropout early.	23:59 of the day of study termination (date of last contact)

The last phase, whichever it is for a subject, always ends on 23:59 of the day of study termination (last contact).

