**Table 3: Laboratory Parameters: Criteria for Markedly Abnormal Values**

Laboratory Parameter	Markedly Low	Markedly High
Albumin (g/L)	<20	> 2 x ULN
Alkaline phosphatase (U/L)	N/A	> 1.5 x ULN
Alanine aminotransferase (ALT) (U/L)	N/A	> 3 x ULN
Aspartate aminotransferase (AST) (U/L)	N/A	> 3 x ULN
Bicarbonate [mmol/L]	15.1	34.9
Bilirubin (umol/L)	N/A	> 1.5 x ULN
Urea Nitrogen (mmol/L)	N/A	> 3 x ULN
Calcium (mmol/L)	<1.75	>3
Chloride (mmol/L)	<90	>120
Creatine kinase (U/L)	N/A	> 3 x ULN
Creatinine (umol/L)	N/A	> 1.5 x ULN
Gamma glutamyl transferase (U/L)	N/A	> 3 x ULN
Glucose (mmol/L)	<3.33	> 3 x ULN
Lactate dehydrogenase (U/L)	N/A	> 1.5 x ULN
Phosphate (mmol/L)	<0.484	> 1.5 x ULN
Potassium (mmol/L)	<2.8	>5.8
Protein (g/L)	N/A	> 2 x ULN
Prothrombin International Normalized Ratio	N/A	≥1.3
Sodium (mmol/L)	<125.0	>155.0
Hemoglobin (g/L)	<75	> 1.1 x ULN
Platelets (x10e9/L)	<100	> 3 x ULN
Erythrocytes (x10e12/L)	<3	> 2 x ULN
Leukocytes (x10e9/L)	<2.5	> 2.5 x ULN
Hematocrit [fraction]		
male	0.24	0.55
female	0.28	0.5

Graphical presentations will be created for the following liver function tests: alanine aminotransferase, aspartate aminotransferase, albumin, bilirubin, alkaline phosphatase, gamma glutamyl transferase. Liver function test results standardized to the upper limit of normal (based on central laboratory ranges) will be graphically presented over time for each subject. The incidence of liver function tests above the central laboratory normal limit will be presented by treatment group at each scheduled time point and endpoint.

Graphical presentations will also be created for prothrombin international normalized ratio results.

Clinical laboratory tests that meet the criteria for abnormal and markedly abnormal will be listed by subject. Results on urine drug screen, alcohol screen and pregnancy test will be presented in separate listings.

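### The TEMA rule in SAP 5.3 can leave out liver enzymes that rise further from an above-range baseline, so the only by-arm count at ALT/AST > 3 x ULN may be too low; bilirubin > 2 x ULN and transaminases 5 x ULN have no by-arm count

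*SAP*

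**What the plan says.** **The TEMA rule (SAP 5.3).** A value qualifies by one of two routes. The first is "based on baseline value (in any period) being missing or within the normal range and the corresponding post baseline value being markedly high/low". The second is a move from below the lower limit to above the upper limit, or the reverse. Table 3 sets markedly high at > 3 x ULN for ALT and AST and > 1.5 x ULN for bilirubin. TEMA incidence is shown by treatment group and study period.

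**Baselines (SAP 2.4).** They are reset: "for each of the Lead-in, DB Treatment and Withdrawal Period, the reference assessment, i.e. baseline, is the measurement the closest" before first dosing in that period. The opening sentence of SAP 5.3 uses the same idea for its summaries: "descriptive statistics on actual values and changes from respective period baseline at each scheduled time point".

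**Other planned laboratory displays.**
- Shift tables: "Cross-tabulations (with classes for below, within, and above the central laboratory range) showing the shift of laboratory values".
- Liver incidence: "The incidence of liver function tests above the central laboratory normal limit will be presented by treatment group".
- Descriptive statistics (SAP 2): "number of observations, mean, standard deviation (SD), standard error (SE), minimum, median and maximum".
- Listings: "Clinical laboratory tests that meet the criteria for abnormal and markedly abnormal will be listed by subject", together with per-subject liver plots standardised to ULN.
- Protocol 11.3: counts below or above the reference range.

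**Limits and entry in the protocol.** Section 3.3.1 uses confirmed ALT/AST > 3 x ULN and confirmed total bilirubin > 2 x ULN as individual stopping criteria. Section 3.3.2 names a 5-fold transaminase elevation over ULN as a reason to set up a data review committee. Exclusion criterion 10.1 bars liver analytes only above 1.5 x ULN at screening. Inclusion criterion 9 admits out-of-range results judged not clinically significant.

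**The concern.** Neither TEMA route covers further worsening in the same direction. A subject who starts a period above ULN and then passes 3 x ULN is not new from normal and has not crossed the range.

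Protocol 16.1 names transaminase elevation as the safety signal from Phase 1 and builds its risk mitigation around it. The primary objective includes overall safety and tolerability (SAP 1.1). A reader of the TEMA table would naturally take it as the number of subjects per arm who reached > 3 x ULN, and it may be lower than that. Incidence is based on all subjects in the treatment group (SAP 2), so an uncounted case stays in the denominator and lowers the reported figure. For the protocol's other two liver limits, no planned table gives a count for either arm.

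**Working it through.** The documents give no figure to reproduce here. The check is to apply the rule as written and then see whether another display fills the gap.

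**1. The rule applied to ALT/AST, in multiples of ULN, period-specific reading**

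| Period baseline | Later value 3.1 | 5.1 | 10 |
|---|---|---|---|
| missing | counted | counted | counted |
| 0.8 or 1.0 | counted | counted | counted |
| 1.01, 1.2, 1.5, 2.0 or 2.9 | not counted | not counted | not counted |

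The same happens for bilirubin: from a baseline of 1.2, a later 2.1 is not counted.

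**2. Can such baselines occur?** Yes. Values up to 1.5 x ULN pass criterion 10.1. From a baseline between 1.0 and 1.5 x ULN, reaching 3 x ULN is a rise of 3/1.0 = 3.0-fold to 3/1.5 = 2.0-fold, so an omitted case from a baseline in that range is a real increase.

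**3. The two readings of *in any period*.** Period-specific: the baseline of the period being tabulated must be missing or normal. Looser: one normal baseline in some period is enough. The reference to the corresponding post-baseline value, the resetting in SAP 2.4 and the opening of SAP 5.3 favour the first, but the TEMA sentence does not say so. Subjects above range at every baseline are missed under both.

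**4. The withdrawal period, if the period-specific reading is intended.** Its baseline follows six weeks of randomised treatment. Take ALT of 0.8 x ULN at the lead-in and double-blind baselines, 2.2 at Week 6 and 3.2 at Day 77. In the double-blind period, 2.2 does not exceed 3. In withdrawal, the baseline of 2.2 is not normal. The subject is TEMA in no period although both pre-drug baselines were normal. Under the looser reading the Day 77 value could count.

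**5. Does another by-arm display give the count?**
- The shift table has three classes, so 1.3 to 1.4 and 1.3 to 10 x ULN fall in the same cell.
- The liver incidence table and Protocol 11.3 cut at the normal limit.
- A descriptive maximum shows that someone reached a value, not how many.

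TEMA is therefore the only by-arm count at > 3 x ULN.

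**6. The other two limits.** From a normal baseline, bilirubin of 1.6 and of 2.1 x ULN fall in the same TEMA count, as do ALT of 3.1 and of 5.1 x ULN. Counts at 2 x and 5 x ULN cannot be recovered.

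**7. Weight of one case.** By the planning figures, 140 x 0.90 / 2 = 63 subjects per arm, and 1/63 = 1.6 percentage points. With 143 entering, 143 x 0.90 / 2 = 64.35, and 1/64.35 = 1.55 points.

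**The case against.** **TEMA is meant to be selective.** Requiring a normal or missing baseline is what makes a value emergent, and the SAP does not present TEMA as absolute incidence. That stands as a defence of the definition, which can stay. It does not supply a count of subjects reaching 3 x ULN.

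**The cases surface elsewhere.** This also stands. Protocol 9.2.6 requires clinically relevant laboratory changes to be recorded as adverse events. SAP 5.2 counts events that are new or increased in severity, by arm and period, with no normal-baseline condition. A confirmed value > 3 x ULN leads to discontinuation under Protocol 3.3.1, and SAP 3.2 summarises withdrawals and termination reasons by treatment group. Listings and ULN-standardised plots show the values themselves. A reader might infer that liver cases would go undetected; the documents do not support that. These displays still do not count subjects at a stated multiple of ULN.

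**The 2 x and 5 x ULN limits are a matter of granularity.** From a normal baseline, every bilirubin above 2 x ULN is inside the > 1.5 x count, and every transaminase above 5 x is inside the > 3 x count. The 5-fold limit is a trigger for a possible committee, whose charter is a separate document not available here. This weakens the point without removing it, because the number at the protocol's own limits still cannot be read from any planned table.

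**The withdrawal pattern is unlikely.** All subjects take placebo in that period, and Phase 1 elevations returned to normal after dosing ended (Protocol 1.1 and 16.1). The Week 6 value in the example would also already appear as a shift and as a value above ULN. The example shows how one reading works; it is not a forecast.

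**Conclusion.** The point holds and is minor. The planned by-arm count at ALT/AST > 3 x ULN can understate how many subjects reached that limit, and the protocol's bilirubin > 2 x ULN and transaminase 5 x ULN limits have no by-arm count. Under the period-specific reading this affects anyone above ULN at that period's baseline; under the looser reading, only subjects above range at every baseline.

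Three stronger inferences are not supported:
- *The comparison between arms is biased.* Not for the double-blind period. SAP 1.2 states "The first period is a placebo lead-in of 3 weeks for all subjects", so a raised double-blind baseline precedes randomised drug and the omission is balanced in expectation.
- *A stated share of cases is lost.* The documents do not give the proportion above ULN at any baseline. The Phase 1 figures in Protocol 16.1 (5 of 30 on drug, 1 of 10 on placebo, up to 2.5 x ULN) are elevations after dosing, not raised baselines, and none reached 3 x ULN. The number affected cannot be derived and may be near zero.
- *Worsening from a raised baseline is never counted.* That is certain only under the period-specific reading.

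Primary efficacy is unaffected.

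**What to change.** 1. Add one table by treatment group and study period counting subjects by maximum post-baseline ALT and AST (> 3 x and > 5 x ULN) and total bilirubin (> 2 x ULN), regardless of baseline. Show the baseline category (normal, above ULN) alongside. For the withdrawal period, also show the double-blind baseline category.
2. State in SAP 5.3 which baseline *in any period* means. The TEMA definition can otherwise remain, and no clinical limit changes.

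The cost is one table and a few words. The table may include small rises from an already raised baseline, for example 2.9 to 3.1 x ULN in withdrawal; the baseline category lets the reader separate these.
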